8.4 EXPEDITED REPORTING OF ADVERSE EVENTS

BI is responsible to fulfil their legal regulatory reporting obligation and in accordance to the requirements defined in this CTP.

[figure not shown]

### **3. INTRODUCTION**

As per ICH E9 ([1](#)), the purpose of this document is to provide a more technical and detailed elaboration of the principal features of the analysis described in the revised CTP, and to include detailed procedures for executing the statistical analysis of the primary and secondary variables and other data.

This TSAP assumes familiarity with the CTP and its amendments. In particular, the TSAP is based on the planned analysis specification as written in CTP Section 7 "Statistical Methods and Determination of Sample Size". Therefore, TSAP readers may consult the CTP for more background information on the study, e.g., on study objectives, study design and population, treatments, definition of measurements and variables, planning of sample size, randomisation.

Study data will be stored in a trial database within the Oracle ClinicalTM system.

The statistical analyses will be performed within the validated working environment CARE, including SASTM (current Version 9.4, by SAS Institute Inc., Cary, NC, USA), and a number of SASTM-based tools (e.g., macros for the analyses of AE data or laboratory data; Report Appendix Generator system (RAGe) for compilation/formatting of the CTR appendices).

PK parameters will be calculated using Phoenix WinNonlinTM software (version Phoenix 6.3, Certara USA Inc., Princeton, NJ, USA) and SASTM (current Version 9.4, by SAS Institute Inc., Cary, NC, USA).

#### **4. CHANGES IN THE PLANNED ANALYSIS OF THE STUDY**

All other analyses described in this TSAP are in accordance with the statistical methods described in the revised CTP.

Additionally a sensitivity analysis will be performed for relative bioavailability with subject as fixed effect.

## **5. ENDPOINTS**

### **5.1 PRIMARY ENDPOINT**

Primary endpoint is the number of subjects with drug-related AEs in the SRD (single rising dose) part of the trial, as defined in Section 5.2.1 of the CTP.

### **5.2 SECONDARY ENDPOINTS**

#### **5.2.1 Key secondary endpoint**

Not applicable.

#### **5.2.2 Secondary endpoints**

Secondary endpoints of this trial are  $AUC_{0-\infty}$  and  $C_{max}$  of BI 894416 in plasma for the SRD part and  $AUC_{0-tz}$ ,  $AUC_{0-\infty}$  and  $C_{max}$  of BI 894416 in plasma for rel. BA (relative bioavailability) part, as defined in Section 5.5.1.1 of the CTP.

## **6. GENERAL ANALYSIS DEFINITIONS**

### **6.1 TREATMENTS**

For basic study information on treatments to be administered, assignment of treatment groups, and selection of doses, cf. Section 4 of the CTP.

Subjects were planned to be treated with

SRD part:

- either a single dose of 3, 10, 20, 30, 40, 54 or 70 mg of BI 894416 (test treatments)  
or
- a single dose of placebo (reference treatment)

All placebo subjects will be analysed in one pooled placebo group (i.e. no distinction between dose groups will be made for placebo subjects).

Rel BA part:

- a single dose of 10 mg BI 894416 as tablet formulation (treatment X)  
and
- a single dose of 10 mg BI 894416 as oral solution formulation (treatment Y)  
and
- a single dose of 40 mg BI 894416 as tablet formulation (treatment Z)

In treatment periods 1 and 2, the sequence of administration of treatments X and Y is assigned in a randomised manner. In the last (third) treatment period, subjects will receive a single dose of 40 mg BI 894416 as tablet formulation. This treatment period follows in a fixed sequence after the first two treatment periods for all subjects.

Analysis phases for statistical analysis of AEs, safety laboratory data, vital signs and ECG are defined for each subject as described in [Table 6.1: 1](#).

Table 6.1: 1 Flow chart of analysis phases for statistical analyses of AEs, safety laboratory data, vital signs and ECG

## SRD part:

Study analysis phase	Label	Start (inclusive)	End (exclusive)
Screening	Screening	Date of informed consent	Date/time of first administration of study drug
On-treatment	Pbo, 3 mg BI, 10 mg BI, 20 mg BI, 30 mg BI, 40 mg BI, 54 mg BI or 70 mg BI, respectively	Date/time of administration of study drug	12:00 a.m. on day after subject's trial termination date

## rel. BA part:

Study analysis phase	Label	Start (inclusive)	End (exclusive)
Screening	Screening	Date of informed consent	Date/time of first administration of study drug
On-treatment	10 mg BI tablet 10 mg BI PfOS 40 mg BI tablet	Date/time of administration of study drug	Drug administration of study drug in next period or 12:00 a.m. on day after subject's trial termination date

CTR Section 15, Appendix 16.1.13.1.8.2 and Appendix 16.1.13.1.8.3 AE displays will present results for the on-treatment phase only.

In CTR Section 15 AE tables (but not in Appendix 16.1.13.1.8.2 and Appendix 16.1.13.1.8.3 AE tables), the following totals will be provided in addition:

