The rel BA trial part will be started (i.e., dosing in rel BA part will be started) after availability of preliminary PK and safety data of the 70 mg dose group of the SRD trial part.

The rel BA part consists of three treatment periods, and all entered subjects are planned to participate at all three treatment periods. Treatments are open-label. In periods 1 and 2, the subjects will receive the treatments X (one single dose of 10 mg BI 894416, tablet formulation, fasting conditions) and Y (one single dose of 10 mg BI 894416, oral solution formulation, fasting conditions) in a randomized two-way crossover fashion. These two periods are followed, after documented review of PK and safety data of periods 1 and 2 of the rel BA part, by treatment Z (one single dose of 40 mg BI 894416, tablet formulation, fasting conditions).

The subjects will be randomly allocated to the two treatment sequences (X-Y-Z or Y-X-Z).

The decision to start treatment in the rel BA part (i.e. to administer treatment in period 1) will be based upon the safety, tolerability, and pharmacokinetic data of the available dose groups of the SRD part including also the 70 mg dose group.

The decision to administer treatment in period 3 of the rel BA part will be based upon the safety, tolerability, and pharmacokinetic data of the SRD part including also the 70 mg dose group and of periods 1 and 2 of the rel BA part.

Proprietary confidential information © 2018 Boehringer Ingelheim International GmbH or one or more of its affiliated companies

Treatment in the rel BA part (i.e. treatment in period 1) will only be started if, in the opinion of the investigator and the trial clinical monitor (or authorised deputies), no safety concerns arose in the preceding dose groups of the SRD part (i.e. no dose-limiting events occurred) and if none of the pre-specified trial-specific stopping criteria were met (refer to [Section 3.3.4.2](#)).

Treatment in period 3 of the rel BA part will only be started if, in the opinion of the investigator and the trial clinical monitor (or authorised deputies), no safety concerns arose in the preceding dose groups of the SRD part or in periods 1 and 2 of the rel BA part (i.e. no dose-limiting events occurred) and if none of the pre-specified trial-specific stopping criteria were met (refer to [Section 3.3.4.2](#)).

If it is decided, based on the criteria above, that treatment in period 3 is not given, no further procedures in period 3 are to be done;

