7.3.3 Safety analyses

Safety will be assessed for the endpoints and parameters of interest listed in [Section 5.2.1](#). All treated subjects (that is, all subjects who received at least one dose of study drug), will be included in the safety analysis. Safety analyses will be descriptive in nature and will be based on BI standards. No hypothesis testing is planned.

Treatments will be compared in a descriptive way. For the SRD part, the placebo control group in the safety evaluation will consist of all placebo treated subjects, regardless of the dose group in which they were treated. Treatment groups will be compared in a descriptive way. Tabulations of frequencies/proportions will be used for the evaluation of categorical (qualitative) data, and tabulations of descriptive statistics will be used to analyse continuous (quantitative) data.

The analyses will be done by 'treatment at onset'.

Measurements (such as ECG, vital signs, or laboratory parameters) or AEs will be assigned to treatments (see [Section 4.1](#)) based on the actual treatment at the planned time of the measurement or on the recorded time of AE onset (concept of treatment emergent AEs). Therefore, measurements planned or AEs recorded prior to first intake of trial medication will be assigned to 'screening', those between trial medication intake in a period until trial medication intake in the next period or the trial termination date will be assigned to the treatment period. These assignments including the corresponding time intervals will be

defined in detail in the TSAP. Please note that AEs occurring after the last per protocol contact but entered before database lock will be reported to drug safety only and will not be captured in the trial database.

Additionally, further treatment intervals (analysing treatments) may be defined in order to provide summary statistics for time intervals, such as combined treatments, on-treatment totals or periods without treatment effects (such as screening and follow-up intervals).

Adverse events will be coded using the Medical Dictionary for Regulatory Activities (MedDRA). Frequency, intensity and causal relationship of AEs will be tabulated by treatment, system organ class and preferred term. SAEs, AESIs (see [Section 5.2.2.1](#)) and other significant AEs (according to ICH E3) will be listed separately.

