7.3.4 Preliminary analyses

Preliminary PK analyses

In contrast to the final PK calculations, the preliminary analysis will be based on planned sampling times rather than on actual times, regardless of whether actual times were within the time windows or not. Therefore, minor deviations of preliminary and final results may occur. The preliminary analysis will provide individual and mean concentration-time profiles and summary statistics of individual values. The preliminary results will be distributed to the Investigator and the trial team.

Depending on the results of available preliminary PK analyses, the tolerability and safety of the compound, and changes of dosing schedule (e.g. additional intermediate doses) additional PK preliminary analysis may be performed based on the request of the Trial Clinical Monitor, the investigator, or Trial Clinical Pharmacokineticist. No formal preliminary PK report will be written.

SRD part

A preliminary analysis of PK parameters (AUC_{0-24} and C_{max} of BI 894416) provided as individual values and geometric means will be performed for each dose level before proceeding to the next level.

Proprietary confidential information © 2018 Boehringer Ingelheim International GmbH or one or more of its affiliated companies

Data from at least 4 actively dosed subjects at the current dose level (dose level N) are required in order to proceed to the next dose level (dose level N+1).

For escalation from Dose Group 1 to Dose Group 2, preliminary PK data are not required.

No inferential statistical interim analysis is planned. However, after each dose group the investigator (or his deputy) is allowed to postpone further dose progression until a preliminary analysis of the data already obtained has been performed.

Rel BA part

A preliminary analysis of PK parameters (AUC_{0-24} and C_{max} of BI 894416) provided as individual values and geometric means will be performed for the current dose group in the SRD part before proceeding to the rel BA part (i.e., before dosing of subjects in the rel BA part in period 1).

In addition, a preliminary analysis of PK parameters (AUC_{0-24} and C_{max} of BI 894416) of periods 1 and 2 of the rel BA part provided as individual values and geometric means will be performed before proceeding to dosing of subjects in period 3 of the rel BA part.

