Data from at least 4 actively dosed subjects at the current dose level of the SRD part are required in order to proceed to the rel BA part, and data from at least 6 subjects dosed in periods 1 and 2 of the rel BA part need to be available in order to proceed to dosing in period 3 of the rel BA part.

Adjusted gMean ratios will be calculated for the preliminary PK parameters obtained for treatment 10 mg BI 894416 tablet compared to PfOS during treatment period 1 and 2 based on the statistical model for assessment of relative bioavailability described in [Section 7.3.2](#).

Furthermore, expected gMean exposure values (C_{max} and AUC_{0-24}) will be predicted for treatment with 40 mg BI 894416 tablet.

No inferential statistical interim analysis is planned. However, the investigator (or his deputy) is allowed to postpone period 3 of the rel BA part until a preliminary analysis of the data already obtained has been performed.

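### The rel BA adverse event phases end at the next dose or at trial termination, so the rule does not equalise follow-up between the 40 mg tablet and the 10 mg treatments

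*SAP*

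**What the plan says.** SAP 6.1, Table 6.1: 1 (rel. BA part), starts each on-treatment phase at dosing and ends it at "Drug administration of study drug in next period or 12:00 a.m. on day after subject's trial termination date". Protocol 7.3.3 has the same rule: events "until trial medication intake in the next period or the trial termination date will be assigned to the treatment period". Neither gives a fixed number of days after dosing.

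The design fixes which event closes which phase. Subjects follow X-Y-Z or Y-X-Z, randomised 1:1 (Protocol 3.1 and 7.5), so the 10 mg tablet (X) and 10 mg solution (Y) share periods 1 and 2, and the 40 mg tablet (Z) is only ever in period 3. Treatment Z comes "after documented review of PK and safety data of periods 1 and 2 of the rel BA part" (Protocol 3.1). The preliminary PK analysis of those periods "will be performed before proceeding to dosing of subjects in period 3 of the rel BA part" (Protocol 7.3.4).

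On reporting, SAP 7.8.1 counts subjects with AEs, and SAP 7 takes percentages over all subjects in the set. Protocol 7.3.3 states: "Treatments will be compared in a descriptive way". Safety and tolerability is an additional objective of the rel BA part (Protocol 7.1.1). Protocol 5.2.2.2 treats every AE up to the end-of-trial examination as on treatment, because the residual effect period is unknown. Protocol 7.3.3 also allows further analysis intervals, including follow-up intervals; the available SAP text defines none of a common length for the rel BA part.

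**The concern.** The chance that a subject has at least one AE grows with the time he is observed, even if the drug does nothing. If the three treatments are watched for different lengths of time, the percentages differ for that reason alone.

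The phases close on different events: period 1 at the second dose, period 2 at the third dose (after the required review), period 3 at trial termination. Time spent waiting for the review counts towards whichever 10 mg treatment was given in period 2. If that wait is long, background events raise the 10 mg columns and the 40 mg tablet looks relatively better. If the interval from the third dose to trial termination is the longer one, the bias runs the other way. At stake is the reading of the 40 mg tablet against 10 mg in a table where each column will hold few events.

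**Working it through.** The documents state no phase length, AE rate or power for this point, so there is no figure of the plan to reproduce. What follows is an illustration under stated assumptions.

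**From the documents:** 12 subjects in the rel BA part (Protocol 7.6); 1:1 sequences (Protocol 7.5); 40 mg always in period 3 (Protocol 3.1, SAP 6.1); phase ends as in SAP Table 6.1: 1.

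**Assumed:**
- w, days from dose 1 to dose 2, and the basic interval from dose 2 to dose 3: 4 to 14
- r, extra days in period 2 for the review: 0 to 21
- f, days from dose 3 to trial termination: 7 to 14
- h, hazard of a first background AE, unrelated to drug: 0.01 or 0.02 per day

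**Formulas.** The probability of at least one background AE in t days is P(t) = 1 - exp(-h × t).
- Each 10 mg treatment: ½ P(w) + ½ P(w + r), since half the subjects receive it in each of periods 1 and 2.
- 40 mg: P(f).
- Mean follow-up is w + r/2 for each 10 mg treatment and f for 40 mg.

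**One case in full** (h = 0.01, w = 7, r = 14, f = 7): P(7) = 1 - exp(-0.07) = 6.8%; P(21) = 1 - exp(-0.21) = 18.9%. The 10 mg column is (6.8 + 18.9)/2 = 12.9%, the 40 mg column is 6.8%, and the difference is -6.1 points.

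| Days in periods 1/2/3 | h per day | Each 10 mg | 40 mg | 40 mg minus 10 mg (points) |
|---|---|---|---|---|
| 7/7/7 | 0.01 | 6.8% | 6.8% | 0.0 |
| 7/21/7 | 0.01 | 12.9% | 6.8% | -6.1 |
| 7/21/14 | 0.01 | 12.9% | 13.1% | +0.2 |
| 7/7/14 | 0.01 | 6.8% | 13.1% | +6.3 |
| 7/21/7 | 0.02 | 23.7% | 13.1% | -10.6 |
| 7/7/14 | 0.02 | 13.1% | 24.4% | +11.4 |
| 14/35/7 | 0.02 | 37.4% | 13.1% | -24.3 |
| 4/4/14 | 0.02 | 7.7% | 24.4% | +16.7 |

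The last two rows are the extremes over the assumed ranges. The difference rises with f and falls with w and r, so the extremes lie at the corners. In subjects, -24.3 points is 0.243 × 12 = 2.9 and +16.7 points is 0.167 × 12 = 2.0; the -6.1 case is 0.7 of a subject.

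In every row the 10 mg tablet and 10 mg solution have the same expected value.

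**With one common window** of, say, 7 days, all three treatments have the same expected background percentage (6.8% at h = 0.01, 13.1% at h = 0.02), and the length-driven difference is zero.

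**The case against.** The strongest reply is that the timing is not visible here. Dosing intervals and end-of-trial timing belong to the Flow Chart, and SAP 6.1 leaves technical detail to an ADS Plan that is also not available. The planned intervals may be similar, and the artefact may then be close to zero. This stands, and it is why only the analysis rule can be criticised, not the actual follow-up.

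Several stronger readings are tempting and are not supported:
- **That the phases are open-ended.** Each is bounded by the next dose or by trial termination.
- **That nothing makes them equal.** The Flow Chart may do so in plan; what can be said is that the SAP rule does not.
- **That the investigator may delay period 3 at will, stretching period 2 further.** Protocol 7.3.4 says the investigator "is allowed to postpone period 3 of the rel BA part until a preliminary analysis of the data already obtained has been performed". That analysis is required before period 3 anyway, so the clause adds no separate delay.
- **That the formulation comparison is biased.** Both 10 mg treatments are spread equally over periods 1 and 2.

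Two further replies carry weight. The long phase is deliberate, because the residual effect period is unknown (Protocol 5.2.2.2); a shorter window should therefore not replace the main table. And late background events may be judged unrelated, since Protocol 5.2.2.1 lists an implausible time to onset as an argument against causality. SAP 7.8.1 tabulates drug-related AEs separately, so that table should be less exposed than the all-cause table modelled above.

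Finally, Protocol 7.3.3 permits extra intervals and does not require them. Leaving them out breaks no rule of the plan; adding them is an improvement.

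**Conclusion.** The concern holds in a limited form. The SAP rule does not equalise AE follow-up between the 40 mg tablet and the 10 mg treatments, and the available text has neither a common window nor an exposure adjustment to compensate. Whether this produces a visible artefact, and in which direction, cannot be told without the planned intervals. The range of -24.3 to +16.7 points rests wholly on assumed hazards and day counts, and zero lies inside it. A reader might infer that the plan makes the 40 mg tablet look safer; the documents do not show that, because the sign is unknown.

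Severity is minor. The comparison is descriptive and untested, the primary endpoint belongs to the SRD part, and 12 subjects give little precision in any case: the exact 95% confidence interval for 2 of 12 is 2% to 48%. Equal windows would not make 40 mg versus 10 mg a clean dose comparison either, because 40 mg always comes third and dose stays confounded with period.

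**What to change.** In SAP 6.1 and 7.8.1, for the rel BA part:

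1. Keep the full-phase AE table as the main table, in line with Protocol 5.2.2.2.
2. Add a supplementary AE table over one post-dose window common to all three treatments. Set its length to the shortest planned interval among dose 1 to dose 2, dose 2 to dose 3, and dose 3 to end of trial. Show later AEs in a separate follow-up column, as Protocol 7.3.3 allows.
3. Report phase duration by treatment, so that readers can see whether follow-up differed.
4. State that 40 mg versus 10 mg remains confounded with period. Also state that, if period 3 is not given, the period 2 phase runs to trial termination.

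The cost is some SAP wording, one extra AE table and a short summary of phase durations, all from dosing and AE onset times already collected. Nothing changes for subjects or visits. The downside is that late events leave the common-window columns; they remain in the follow-up column and in the main table.

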## SRD:

- **"Total BI"**, defined as the total over all on-treatment phases involving BI

## rel. BA part:

- **"Total on-trt"**, defined as the total over all on-treatment phases

CTR Appendix 16.1.13.1.8.1 displays will present results for the screening and on-treatment phases.

Additionally to the totals defined above, the following total will be provided in CTR Section 16.1.13.1.8.1 AE tables:

- **"Total"**, defined as the total over all study phases (screening + on-treatment)

- "Study Total", defined as the total over all study phases (screening +on-treatment) for the SRD and rel. BA part combined (only for disclosure outputs)

More details on the technical implementation of these analyses are provided in the ADS Plan of this TSAP.

## 6.2        IMPORTANT PROTOCOL DEVIATIONS

Consistency check listings (for identification of violations of time windows) and a list of protocol deviations (e.g. deviations in drug administration, in blood sampling times, etc.) will be provided to be discussed at the RPM/DBLM. At this meeting, it will be decided whether a discrepant data value can be used in analyses or whether it must be corrected in the clinical database. Each protocol deviation must be assessed to determine whether it is an IPD. For definition of IPDs, and for the process of identification of these, refer to the BI reference document " Identify and Manage Important Protocol Deviations (iPD)", " [\(2\)](#) .

Table 6.2: 1    Important protocol deviations

Category / Code	Description
A	Entrance criteria not met
A1	Inclusion criteria violated
A2	Exclusion criteria violated
B	Informed consent
B1	Informed consent not available
B2	Informed consent too late
C	Trial medication and randomisation
C1	Incorrect trial medication taken
C2	Randomisation not followed
C5	Improper washout between treatments
C6	Incorrect dose of trial medication
D	Concomitant medication
D1	Prohibited medication use
E	Missing data
	None 
G	Other trial specific important violations
G1	Certain violations of procedures used to measure secondary PK data

Deviations C1, C2 and G1 can only be detected at the trial site.

 Missing visits, evaluations, and tests will be considered missing data, not IPDs

Source: BI reference document " Identify and Manage Important Protocol Deviations (iPD)", " [\(2\)](#) .

If any IPDs are identified, they are to be summarised into categories and will be captured in the RPM/DBLM minutes via an accompanying Excel spreadsheet [\(3\)](#) . The table above contains the categories which are considered to be IPDs in this trial. IPD C5 is only applicable

for the SRD part. If the data show other IPDs, this table will be supplemented accordingly by the time of the RPM/DBLM.

IPDs will be summarised and listed.

